12.1 RESEARCH PARTICIPANT REGISTRATION AND RANDOMIZATION PROCEDURES

12.2 Research Participant Registration

Confirm eligibility as defined in the section entitled Criteria for Patient/Subject Eligibility.

Obtain informed consent, by following procedures defined in section entitled Informed Consent Procedures.

During the registration process registering individuals will be required to complete a protocol specific Eligibility Checklist.

All participants must be registered through the Protocol Participant Registration (PPR) Office at Memorial Sloan-Kettering Cancer Center. PPR is available Monday through Friday from 8:30am – 5:30pm at [contact]. Registrations must be submitted via the PPR Electronic Registration System (<http://ppr/>). The completed signature page of the written consent/RA or verbal script/RA, a completed Eligibility Checklist and other relevant documents must be uploaded via the PPR Electronic Registration System.

12.3 Randomization

Participants will be randomized to one of the two 7-week interventions (Individual Meaning Centered Psychotherapy or Supportive Individual Psychotherapy) or the Enhanced Usual Care. After eligibility is confirmed and immediately after consent is obtained, patients will be registered in the MSKCC Protocol Participant Registration (PPR) system and randomized using the MSKCC Clinical Research Database (CRDB), by calling the MSKCC PPR Office at [contact] between the hours of 8:30 am and 5:30 pm, Monday - Friday.

Randomization is overseen by the MSKCC Biostatistics Service. Randomization will be accomplished by the method of random permuted block, and stratified by two dichotomized variables: 1) baseline Distress Thermometer (4 through 6 vs. 7 through 10); and 2) baseline Karnofsky score (60 through 79 vs. 80 or greater).

Patients who are registered and randomized, but cannot make their scheduled session time (because of conflict or illness) will be placed on a waitlist so they can be offered a spot when they are available in the future, in the same treatment assignment as randomized.

13.1 DATA MANAGEMENT ISSUES

A Research Study Assistant (RSA) will be assigned. The responsibilities of the RSA include project compliance, data collection, abstraction and entry, data reporting, regulatory monitoring, problem resolution and prioritization, and coordinating the activities of the protocol study team. The data collected for this study will be entered into a secure database, the hard copies of the questionnaires will be kept in a locked, secured location and will only be accessible to study staff. Data will be stripped of any identifying information. A list, matching participants' names and case numbers will also be kept in a secure area at MSKCC. All questionnaire data completed by participants will be identified only with a study code number.

Study findings will be presented in aggregate form only, with no reference made to individual participant's data. The Principal Investigator and his research team will be responsible for identifying, reviewing and reporting all necessary adverse events to the institutional IRB as appropriate. Adverse events are identified through standard, routine protocol review and clinical assessment of each participant in the study. Minimal data set will be maintained in CRDB.

13.2 Quality Assurance

Reports will be generated to monitor patient accruals and completeness of registration data. Data quality reports will be generated to assess missing data and inconsistencies. Accrual rates and extent and accuracy of evaluations and follow-up will be monitored periodically throughout the study period and potential problems will be brought to the attention of the study team for discussion and action. Random-sample data quality and protocol compliance audits will be conducted by the study team.

13.3 Data and Safety Monitoring

The Data and Safety Monitoring (DSM) Plans at Memorial Sloan-Kettering Cancer Center were approved by the National Cancer Institute in September 2001. The plans address the new policies set forth by the NCI in the document entitled —Policy of the National Cancer Institute for Data and Safety Monitoring of Clinical Trials|| which can be found at:

<http://www.cancer.gov/clinicaltrials/conducting/dsm-guidelines/page1>. The DSM Plans at MSKCC were established and are monitored by the Office of Clinical Research. The MSKCC Data and Safety Monitoring Plans can be found on the MSKCC Intranet at:

[http://smskpsps9/dept/ocr/OCR%20Website%20Documents/Clinical%20Research%20Quality%20Assurance%20\(CROA\)/MSKCC%20Data%20and%20Safety%20Monitoring%20Plan.pdf](http://smskpsps9/dept/ocr/OCR%20Website%20Documents/Clinical%20Research%20Quality%20Assurance%20(CROA)/MSKCC%20Data%20and%20Safety%20Monitoring%20Plan.pdf).

There are several different mechanisms by which clinical trials are monitored for data, safety and quality. There are institutional processes in place for quality assurance (e.g., protocol monitoring, compliance and data verification audits, therapeutic response, and staff education on clinical research QA) and departmental procedures for quality control, plus there are two institutional

committees that are responsible for monitoring the activities of our clinical trials programs. The committees: Data and Safety Monitoring Committee (DSMC) for Phase I and II clinical trials, and the Data and Safety Monitoring Board (DSMB) for Phase III clinical trials, report to the Center's Research Council and Institutional Review Board.

During the protocol development and review process, each protocol will be assessed for its level of risk and degree of monitoring required. Every type of protocol (e.g., NIH sponsored, in-house sponsored, industrial sponsored, NCI cooperative group, etc.) will be addressed and the monitoring procedures will be established at the time of protocol activation.

This trial is funded by the NCI/NCH and will comply with all of its requirements for Data and Safety Monitoring. This trial sponsor does not have an independent Data Safety Monitoring Process.

13.4 Regulatory Documentation

Participating sites/investigators who are consulting and/or conducting specimen or data analysis should submit this protocol to their IRB according to local guidelines. Copies of any site IRB correspondence should be forwarded to MSKCC.

14.1 PROTECTION OF HUMAN SUBJECTS

Overall, the benefits of this study outweigh the risks. Patients participating in the study will all have the benefit of receiving seven individual psychotherapy sessions provided by trained staff of the MSKCC Psychiatry Service, free of charge, or a targeted patient referral sheet. The risks are primarily related to the potentially upsetting nature of some of the themes that will be raised in the individual psychotherapy sessions or in the self-report questionnaires which ask about mood, depression, hopelessness and end-of-life care issues

Potential Risks/ Risk Management

Some subjects may become distressed or experience anxiety when discussing end-of-life care issues in the individual psychotherapy sessions. In addition, some patients may become distressed or experience anxiety when filling out the self-report questionnaires which inquire about their illness, degree of depression thoughts on end of life care, feelings of hopelessness, pain and physical symptoms, quality of life and social support. All the psychotherapy individual interventions will be facilitated by highly trained, and qualified mental health professionals who have extensive experience with cancer patients and are sensitive to these issues arising during individual psychotherapy. Therapists will be supervised closely by the P.I., a senior clinician with close to 20 years of experience in the psychiatric care of advanced cancer patients. We will also utilize research staff that is experienced in obtaining research information on issues related to cancer illness and its impact, emotional distress, quality of life, and other issues of a sensitive nature. When necessary, subjects who experience psychological distress related to filling out self-report questionnaires will have appropriate care provided by The MSKCC Psychiatry Service.

There will be only one exception to the strict patient confidentiality policy, described above, which pertains to information obtained during the research assessment, which would indicate that the patient is seriously suicidal and may pose a significant and acute risk of self-harm. Subjects will be informed of this exception, and will also be informed such information will be shared with the P.I.

of the study and their attending physician so that timely and appropriate psychiatric assessment and care can be provided by the MSKCC Psychiatry Service.

Benefits

Patients participating in the study will all have the benefit of receiving a 7-week individual psychotherapy intervention provided by trained staff of the MSKCC Psychiatry Service, free of charge or a targeted referral sheet. Moreover, patients who are identified as having a major psychiatric disorder which would preclude them from participating in the psychotherapy study (e.g., untreated severe major depression requiring treatment) will be referred to the MSKCC Psychiatric Service for timely treatment.

Subject Burden

In an effort to minimize patient burden, the assessment protocol has been designed to be as brief as possible in order to gather the required information. The questionnaires take approximately one hour to complete, depending on the individual patient. Research staff will interrupt an assessment if a patient is fatigued or in significant pain. In an effort to ease patient burden, questionnaires can be mailed to patients, read to patients over the phone, or read to patients in person to help with completion if necessary.

Additionally, for patients who express interest in participating in the study but require financial assistance for transportation to/from individual sessions or to complete assessments, a \$20.00 travel reimbursement per session will be offered.

14.2 Privacy

MSKCC's Privacy Office may allow the use and disclosure of protected health information pursuant to a completed and signed Research Authorization form. The use and disclosure of protected health information will be limited to the individuals described in the Research Authorization form. A Research Authorization form must be completed by the Principal Investigator and approved by the IRB and Privacy Board.

14.3 Serious Adverse Event (SAE) Reporting

Any SAE must be reported to the IRB/PB as soon as possible but no later than 5 calendar days. The IRB/PB requires a Clinical Research Database (CRDB) SAE report be submitted electronically to the SAE Office at [contact]. The report should contain the following information:

Fields populated from CRDB:

- Subject's name (generate the report with only initials if it will be sent outside of MSKCC)
- Medical record number
- Disease/histology (if applicable)
- Protocol number and title

Data needing to be entered:

- The date the adverse event occurred
- The adverse event
- Relationship of the adverse event to the treatment (drug, device, or intervention)

- If the AE was expected
- The severity of the AE
- The intervention
- Detailed text that includes the following
 - A explanation of how the AE was handled
 - A description of the subject's condition
 - Indication if the subject remains on the study
 - If an amendment will need to be made to the protocol and/or consent form.

The PI's signature and the date it was signed are required on the completed report.

Severe distress as a direct result of the intervention, suicide attempt, or expressed suicidal ideation with plan or intent will be considered a serious adverse event and will be reported.

Hospitalizations and death are expected events for all patients involved in this clinical trial; We will not report events that are unrelated to participation in this study.

14.2.1

N/A

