5.0 CRITERIA FOR SUBJECT ELIGIBILITY

5.1 Subject Inclusion Criteria

- 21 years of age and older
- Able to communicate and understand English well enough to complete assessments and intervention**
- Patients with solid tumors with advanced disease (see section 4.1 for more specific description of evidence of advanced disease) receiving ambulatory care at MSKCC*
- Distress Thermometer rating of 4 or greater*

*Patients who do not meet these eligibility criteria may be offered participation as a training case (See inclusion criteria for Training Cases below).

Subject Inclusion Criteria - Training Cases

- 21 years of age and older
- Able to communicate and understand English well enough to complete the intervention**
- Patients with solid tumors with advanced disease (see section 4.1) receiving ambulatory care at MSKCC with a Distress Thermometer rating of 3 or less
 - or
 - Patients with solid tumors who do not meet eligibility criteria for advanced disease receiving ambulatory care at MSKCC
 - or
 - Patients with solid tumors with advanced disease (see section 4.1) receiving ambulatory care at MSKCC who have participated in a prior meaning focused intervention study
 - or
 - Patients with solid tumors with advanced disease (see section 4.1) receiving ambulatory care at MSKCC who have enrolled in this study, been assigned to the EUC arm, and completed all study requirements including follow-up assessments.

**The study treatment manual materials and assessments were designed and validated in English and are not currently available in other languages. Translation of the intervention and questionnaires into other languages would require reestablishing the reliability and validity of them. Therefore, participants must be able to communicate in English.

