8.0 TOXICITIES/SIDE EFFECTS

Minimal risk of psychological distress is posed by study questions that ask participants to identify their current problems. However, since study items were chosen to reflect what are likely to be

existing concerns, the present study is not expected to markedly increase participants' psychological distress above their routine concerns. Experienced personnel, trained in interviewing medically ill individuals, will administer all instruments, and will be supervised by the Principal Investigator or Project Coordinator. Participants' reactions will be observed and signs of significant distress will be followed up by the PI or study therapist with attention to presence of any serious psychological concerns. In the unlikely event of significant acute distress, participants will be referred to a staff member from the Department of Psychiatry and Behavioral Sciences. If a research participant indicates that s/he is acutely suicidal and poses a significant and acute risk of self-harm, this information will be shared with their attending physician so that timely and appropriate psychiatric assessment and care can be provided by the MSKCC Social Work or Psychiatry Service staff.

However, some subjects may become distressed or experience anxiety when discussing end-of-life care issues in the individual psychotherapy sessions or in response to filling out the self-report questionnaires that inquire about their illness, degree of depression, thoughts on end of life care, feelings of hopelessness, pain and physical symptoms, quality of life and social support. All patients will be monitored for severe distress and explicit suicidal ideation with plan or intent at each assessment point (including EUC). We will continue to utilize interviewers who have been trained to be sensitive to the nature of end-of-life care issues. When necessary, subjects who experience psychological distress related to filling out self-report questionnaires will be referred to appropriate care by the MSKCC Psychiatry Service.

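### Section 14.3 calls every hospitalization and death expected and leaves unrelated events out, so reporting of suicide deaths, some psychiatric admissions and events in non-advanced training cases is ambiguous or can lapse

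*Combined protocol and SAP*

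**What the plan says.** Section 14.3 contains three statements that bear on what reaches the IRB/PB.

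- A general duty: "Any SAE must be reported to the IRB/PB as soon as possible but no later than 5 calendar days". It carries no condition on relatedness.
- A list of named events that count as serious and will be reported: "Severe distress as a direct result of the intervention, suicide attempt, or expressed suicidal ideation with plan or intent". The attempt and ideation items have no attribution condition and apply in all arms. The distress item has attribution built in.
- An expectedness statement with a filter: "Hospitalizations and death are expected events for all patients involved in this clinical trial; We will not report events that are unrelated to participation".

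The SAE form in the same section already has separate fields for the relationship of the event to treatment and for whether it was expected.

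Elsewhere, Section 5.1 (training cases) admits "Patients with solid tumors who do not meet eligibility criteria for advanced disease receiving ambulatory care at MSKCC". Section 6.0 says that training cases are consented and receive seven sessions. Section 4.3 says that they are not randomized and complete no assessments. Section 8.0 monitors patients in all arms for severe distress and explicit suicidal ideation at each assessment point. It also recognizes that distress may arise "in response to filling out the self-report questionnaires that inquire about their illness, degree of depression, thoughts on end of life care", and Section 14.1 repeats that risk.

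**The concern.** The trial enrolls patients because they are distressed (Distress Thermometer of 4 or more, Section 5.1), and desire for hastened death is among its primary outcomes (Section 9.1). Suicide and acute psychiatric deterioration are therefore the harms for which the reporting rule most needs to be plain. Section 14.3 is plain about attempts and about ideation with a plan or intent. It is less plain about outcomes at least as serious, because death and hospitalization are handled in a separate sentence that treats them as expected and lets unrelated ones go unreported.

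The rationale for calling these events expected is advanced cancer, yet the statement reaches everyone in the trial, including participants admitted as training cases precisely because their disease is not advanced. At stake is whether the IRB/PB receives a small number of important reports. No efficacy result depends on it.

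**Working it through.** No arithmetic applies. The check is to run each kind of event through the clauses of Section 14.3.

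| Event | Named as always reportable? | Touched by the expected/unrelated sentence? | Result |
|---|---|---|---|
| Non-fatal suicide attempt, any arm | Yes, no attribution condition | No | Reported |
| Ideation with plan or intent, any arm | Yes, no attribution condition | No | Reported |
| Death by suicide | Not by name; a fatal attempt is naturally an attempt | Yes, as a death | Ambiguous |
| Psychiatric admission after an attempt, or with plan or intent | Yes, through the underlying event | Yes, as an admission | Underlying event reported |
| Psychiatric admission without attempt, plan or intent, judged unrelated | No | Yes | Can go unreported |
| Death or admission, judged unrelated, in a training case without advanced disease | No, unless suicidality is involved | Yes, because all patients are included | Can go unreported, on a premise that does not fit |
| Severe distress directly caused by the intervention | Yes | No | Reported |
| Severe distress caused by questionnaires | No | Not removed, since answering them is participation | Not named as serious anywhere |

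Four observations follow.

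1. **Internal conflict.** The opening duty covers any SAE. The closing filter withholds events unrelated to participation. A serious but unrelated event satisfies both sentences, and they give opposite instructions. The section gives no criteria for relatedness and names no one to judge it.
2. **Suicide death and psychiatric admission.** The named list stops at attempt and ideation. The next sentence takes in deaths and hospitalizations of every cause. Nothing says which sentence governs when an event fits both.
3. **Training cases.** Section 5.1 gives several routes to becoming a training case; one of them is disease that does not meet the advanced criteria. For these participants the advanced-cancer reason for expecting death or admission is absent. Because they complete no assessments (Section 4.3), the assessment-point monitoring in Section 8.0 does not reach them, which leaves the SAE rule with more to do.
4. **Severe distress.** Sections 8.0 and 14.1 name two sources of distress, sessions and questionnaires. The named SAE covers only what directly results from the intervention. Attribution thus acts as an entry condition, although the form has a field in which to record it.

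**The case against.** The strongest reply is that the principal harm is already covered. Attempts and ideation with a plan or intent are reported whatever the cause, in all three arms, and Section 8.0 looks for severe distress and suicidal ideation at each assessment, EUC included. This stands. A reader might infer that the IRB would see no signal of suicidality, or that completed suicide is exempt. The documents support neither: a fatal attempt is most naturally read as an attempt, and the fault is that the text does not say so.

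Other strong readings also fail.

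- **Size.** A reader might take the planned loss between entry and follow-up as the group in which events vanish: 138 − 90 = 48 per arm, or 3 × 48 = 144 of 414 (34.8%). That is assessment attrition. Section 10.0 includes voluntary withdrawal and non-compliance among the reasons for leaving, and Section 11.0 links withdrawal to failing health without giving a share. It is not a count of deaths or admissions.
- **EUC.** A reader might infer that EUC cannot generate a severe-distress SAE. Sections 9.1 and 11.0 list EUC among the interventions, so distress arising from its feedback or referrals could qualify. The plan also compares no severe-distress SAE counts between arms.
- **Oversight.** Section 13.3 says "This trial sponsor does not have an independent Data Safety Monitoring Process", but it also describes institutional monitoring committees. A lack of independent oversight does not follow. Section 13.1 makes the investigator's team responsible for identifying, reviewing and reporting events; it does not expressly assign the relatedness judgment.
- **Distress of any cause.** It would be tempting to make all severe distress an SAE. Section 14.3 sets no severity threshold and the population is selected for distress, so the volume could be large. Nothing in the documents calls for this.

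The training-case gap is also narrow: Section 4.3 mentions one or two such cases for some therapists, and some of those patients do have advanced disease.

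**Conclusion.** The concern holds as a defect in the reporting rule. Section 14.3 contradicts itself on serious unrelated events and leaves the classification of suicide death open. It allows a psychiatric admission without attempt, plan or intent to go unreported when judged unrelated, and it applies an advanced-cancer premise to participants who may not have advanced cancer. Its severe-distress item is narrower than the risks named in Sections 8.0 and 14.1.

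The size cannot be stated. The documents give no rate of death, suicide or psychiatric admission and no total number of training cases. The number of affected reports is probably small, but that is a judgment, not a figure from the plan. The conclusion rests on reading Section 14.3 as it stands; the institutional monitoring plan cited in Section 13.3 is not reproduced in the documents and could add requirements. No planned analysis is affected. It should be fixed, but it does not threaten the trial's validity.

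**What to change.** Amend Section 14.3 in three places.

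1. State that death by suicide, and hospitalization for self-harm or for a psychiatric reason, are reported whatever the attribution, as a suicide attempt already is. This also settles which sentence governs when the general duty and the filter disagree on these events.
2. Limit the statement that hospitalization and death are expected to participants who meet the advanced-disease criteria, so that it no longer covers training cases who do not.
3. Reconcile the severe-distress wording with Sections 8.0 and 14.1 so that distress arising from study procedures, questionnaires included, is covered. Record attribution in the existing relationship field.

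The cost is amendment wording in one section and a few more SAE reports. One practical point: the chart review in Section 7.1 collects hospital death and hospitalization near death but does not list cause of death, so the team would have to note the cause when it learns of a death. No assessment, analysis or sample size changes.
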